2.2 Analysis sets

Full Analysis Set

The Full Analysis Set (FAS) comprises all patients to whom study treatment has been assigned and who received one dose of study treatment.

Safety Set

The Safety set is identical as the Full Analysis set in the study. All safety analyses will be done using the Safety Set.

Pharmacokinetic analysis set (PAS)

The Pharmacokinetic analysis set (PAS) includes all subjects who received at least one dose of eltrombopag and have at least one evaluable PK sample. However, only evaluable PK samples will be included in the PK analysis. A concentration will be flagged as NOT evaluable programmatically if any of the following conditions is satisfied:

- The dose received is not the protocol-planned dose in any of the 7 consecutive days prior to the current dose.
- Vomiting occurs within 4 hours of the last dose (pre-dose trough sample).
- Vomiting occurs within 4 hours of the current dose (post-dose samples).

Only PK concentrations/parameters which are not flagged for exclusion programmatically will be used for summaries or statistical analysis. Any concentration listings will include all concentration values, with flags indicating those excluded from analyses.

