### **6.7.2 Instruction for prescribing and taking study treatment**

Eltrombopag will be administered orally, once daily, on an empty stomach (1 hour before or 2 hours after a meal) and at least 2 hours before or 4 hours after any products containing polyvalent cations such as antacids, calcium-rich foods ( $> 50$  mg calcium, e.g., dairy products and calcium-fortified juices), or mineral supplements containing polyvalent cations (e.g. aluminum, calcium, iron, magnesium, selenium, and zinc).

Subjects will be instructed to take eltrombopag daily at the same time each day.

On days that PK samples are obtained, the subject should take eltrombopag during the clinic visit after the pre-dose PK samples and prior to post-dose PK samples, when instructed by the study staff.

If vomiting occurs during the course of treatment, subjects should not take the study drug (eltrombopag) again before the next scheduled dose.

Subjects will be instructed not to make up missed doses. A missed dose is defined as a case when the full dose is not taken within 8 hours of the approximate time of the usual daily dose. That day's dose should be omitted and the subject should continue treatment with the next scheduled dose.

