### 8.5.1.1 Pharmacokinetic blood collection and handling

At least the first 12 subjects starting with 25 mg/day will receive intensive PK sampling over a 24 hour period on Days 14 to 15 after the first dose, to ensure 12 subjects providing evaluable full PK profiles. For this intensive PK sampling, a total of 7 blood samples (2 mL/sample) will be collected at the following time points: pre-dose, and 1, 2, 4, 6, 8, and 24 h post-dose. A full evaluable PK profile is defined as at least 6 of 7 planned PK samples are collected and the subject has not vomited within 4 hours after dose of both PK sampling day and the day before PK sampling day. When these subjects who received intensive PK sampling escalate to higher dose levels (e.g. 50, 75, 100, 125 and up to 150 mg/day), they will provide one blood sampling at pre-dose on the 15th day after each new dose has started.

After the purpose of getting evaluable full PK profiles in 12 subjects has been fulfilled, the rest of subjects will receive sparse PK sampling only. In all remaining subjects, one blood sample each will be collected at pre-dose on the 15th day for the initial 25 mg/day dose and after each new dose has started until the maximal dose is reached.

If a subject meets the criteria for dose reduction and dose is decreased to a lower level which the subject has received previously, no planned PK sample will be collected for new lower doses.

A detailed blood sampling log for PK evaluation is indicated in [Table 8-4](#) Pharmacokinetic log. The time of blood collection will be recorded on the PK blood collection page in the CRF (e.g. the actual date/time of blood samples will be recorded relative to the dose administration). Vomiting information after administration will be collected within 4 hours of dosing. In case of DILI (see [Section 6.5.1.2](#)), an unscheduled eltrombopag PK sample should be collected. On the days of PK collection, the subject will be instructed to take study drug after the pre-dose blood sample is taken.

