2.9 Pharmacokinetic endpoints

PAS will be used in all pharmacokinetic data analyses and PK summary statistics. In the case of samples taken are not within the time windows around the scheduled time points. These samples will exclude from the descriptive statistic which are summarized by time point, but will include in the non-compartmental analysis.

PK summary analyses will not be reproduced for final CSR.

PK parameters for subjects with extensive PK samples

The PK parameters that will be determined are shown in [Table 2-4](#). PK parameters of eltrombopag, including but not limited to those listed in Table 2-4, will be calculated from the individual concentration-time profile obtained following the administration of the study treatment and listed by subject.

Table 2-4 Non-compartmental PK parameters

AUClast	The AUC from time zero to the last measurable concentration sampling time (tlast) (mass*time*volume ⁻¹)
AUCtau	The AUC calculated to the end of a dosing interval (tau) at steady-state (amount*time*volume ⁻¹)
Cmax	The maximum (peak) observed plasma drug concentration after single dose administration (mass*volume ⁻¹)
Tmax	The time to reach maximum (peak) plasma drug concentration after single dose administration (time)
Ctrough	Pre-dose concentration at the end of dose interval (mass*volume ⁻¹)
CLss/F	Apparent systemic (or total body) clearance at steady state from plasma (volume/time)

Descriptive statistics (n, arithmetic mean, CV% mean, standard deviation (SD), median, geometric mean, CV% geo-mean, minimum and maximum) will be presented for PK analysis set for all PK parameters defined above except Tmax, where only n, median, minimum and maximum will be presented.

PK concentrations

Descriptive statistics including mean (arithmetic and geometric), SD, CV (arithmetic and geometric), median, minimum and maximum for PK concentration will be presented by dose, visit/sampling time point, including the frequency (n, %) of concentrations below the LLOQ and reported as zero.

The geometric mean and arithmetic mean (SD) concentration-time profiles will also be graphically presented. In addition, individual concentration-time profiles will be displayed graphically.

[figure not shown]
In addition, PK concentrations of eltrombopag for subjects with sparse PK samples will be summarized by dose, visit and scheduled time point.

All individual plasma eltrombopag concentration data will be listed by dose, visit and scheduled time point.

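### After vomiting on the day before PK sampling, the SAP drops only the pre-dose trough and could keep a lowered profile in Cmax, AUC and CLss/F; separately, a profile ending at 8 h could pass as full and distort AUClast

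*SAP*

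**What the plan says.** Protocol 8.5.1.1 plans seven samples per intensive profile at 25 mg/day: pre-dose, then 1, 2, 4, 6, 8 and 24 h. It sets a condition on the whole profile: "at least 6 of 7 planned PK samples are collected and the subject has not vomited within 4 hours after dose", where the vomiting condition covers both the sampling day and the day before. Any six of the seven satisfy the count. Twelve such profiles end intensive sampling.

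SAP 2.2 has no condition on the profile. A subject enters the PK analysis set with one usable value ("have at least one evaluable PK sample"), and single concentrations are flagged out by three rules:

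- dosing history: "The dose received is not the protocol-planned dose in any of the 7 consecutive days prior to the current dose";
- vomiting after the previous dose: "Vomiting occurs within 4 hours of the last dose (pre-dose trough sample";
- vomiting after the dose on the sampling day: "Vomiting occurs within 4 hours of the current dose (post-dose samples".

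It then states: "Only PK concentrations/parameters which are not flagged for exclusion programmatically will be used for summaries or statistical analysis". No rule for flagging a parameter follows. SAP 2.9 derives Cmax, AUCtau, AUClast, Ctrough and CLss/F for this set without asking for a fully evaluable profile. AUClast is defined there as "The AUC from time zero to the last measurable concentration sampling time (tlast"). Missing PK values are not imputed.

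**The concern.** The two documents apply different units of exclusion. For the protocol, vomiting on the day before disqualifies the profile as fully evaluable. For the SAP, it costs the profile one sample. A subject can therefore fail the protocol's count of 12 and still contribute to the exposure summaries, with a profile that the lost dose has lowered throughout.

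The second gap lies in the count. The 24 h sample is the only one after 8 h. If it is the one missing, the profile still passes the protocol's rule, and its AUClast covers 8 h while the other subjects' covers 24 h.

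The intensive profiles are the trial's only source of AUC and Cmax. Protocol 4.1.2 wants the PK data to help bridge exposure to patients outside China and to allow comparison with Japanese SAA patients. With about 12 profiles, one unsuitable profile shows in the mean.

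**Working it through.** The documents state no figure to reproduce here; protocol 12.8.1 chose 12 profiles on feasibility.

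**Step 1: apply the SAP flags to a Day 14 profile after vomiting within 4 h of the Day 13 dose.**

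| Sample | Dose before it | SAP 2.2 result |
|---|---|---|
| Pre-dose, Day 14 | Day 13 (vomited) | flagged |
| 1, 2, 4, 6, 8 h | Day 14 (kept) | retained |
| 24 h (pre-dose, Day 15) | Day 14 (kept) | retained |

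Six of seven samples survive, so a sample count alone would not catch this profile; the day-before condition is needed. The vomited dose is not replaced (protocol 6.7.2: "If vomiting occurs during the course of treatment, subjects should not take the study drug (eltrombopag) again before the next scheduled dose"). The dosing-history rule asks whether the planned dose was received, and a dose taken and then vomited is not named in it.

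**Step 2: size of the carry-over.** The half-life of 21-32 h comes from protocol 1.3. Assumed: one compartment, first-order absorption with ka 0.5-1.0/h (steady-state peak about 3-4.7 h, within the stated Tmax of 2-6 h), 14 once-daily doses, and a fraction f of the Day 13 dose lost.

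- Single dose: C1(t) = ka/(ka - k) × (e^(-kt) - e^(-ka·t)), with k = ln 2 / half-life.
- Day 14 profile: the sum of C1(t + 24j) for j = 0 to 13. With loss: subtract f × C1(t + 24).

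Hand check with instant absorption and f = 1: the lost share of AUCtau is about e^(-24k) × (1 - e^(-24k)). That is 0.453 × 0.547 = 24.8% at 21 h and 0.595 × 0.405 = 24.1% at 32 h. Slower absorption raises it slightly:

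| Quantity, f = 1 | Share of undisturbed value |
|---|---|
| Flagged trough | 45-59% |
| AUCtau | 73.5-75.3% |
| Cmax | 73.7-75.4% |
| Retained 24 h value | 75-76% |

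So AUCtau and Cmax fall by about 25-27%, and by 12-13% for f = 0.5. CLss/F, which is dose/AUCtau, rises by 1/0.753 - 1 = 33% to 1/0.735 - 1 = 36% for f = 1. If ka is set instead to give a single-dose Tmax of 2-6 h, the full-loss fall is 24-27%.

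Effect of one such profile on a geometric mean of 12: 1 - 0.753^(1/12) = 2.3% to 1 - 0.735^(1/12) = 2.5%.

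**Step 3: a profile ending at 8 h.** One of the seven possible 6-of-7 sets lacks the 24 h sample. In the same model AUC0-8/AUC0-24 is 0.366-0.405.

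- AUClast, one such profile among 12: 1 - 0.405^(1/12) = 7.3% to 1 - 0.366^(1/12) = 8.0% off the geometric mean. Two give 14-15%.
- Cmax: unchanged.
- AUCtau: needs an extrapolation over 8-24 h, for which neither document gives a rule. From the 4-8 h slope it comes out at about 100-109% of the true value.

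**The case against.** The strongest reply is that protocol 8.5.1.1 defines a fully evaluable profile in order to decide when 12 have been collected; it does not say that other profiles must leave the summaries. Protocol 12.1 leaves the definition of an evaluable sample to the SAP, and the SAP supplies one. This stands in part: the SAP does not breach an explicit protocol exclusion. But the delegation concerns samples, the carry-over is pharmacological whatever the definition was for, and SAP section 4 declares no change from the protocol's analyses.

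The dosing-history rule or the reference to flagged parameters might also be used to exclude such a profile. Neither does so as written. If a vomited dose counted as not received, the separate trough rule would be largely redundant.

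Other replies stand. PK is a secondary, descriptive objective. Parameters are listed by subject and flagged concentrations are shown, so a careful reader could spot an affected profile.

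Three stronger readings are tempting and not supported:

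- A reader might infer that both gaps bias exposure low and clearance high. That holds for vomiting on the day before. An 8-hour profile lowers only AUClast; its extrapolated AUCtau need not be low and in the model was at or above the true value.
- A reader might infer that nobody asks for the 24 h sample. Protocol 8.5.1.1 and Table 8-5 schedule it, and it doubles as the Day 15 trough due from every subject, which on the schedule's day count is the Week 2 visit. What is missing is its role as a condition for evaluability.
- A reader might infer that such profiles are in the summaries. The documents give no vomiting or missing-sample rate, so this cannot be said.

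**Conclusion.** The point holds in limited form. As written, SAP 2.2 could keep a profile lowered by vomiting on the day before in Cmax, AUCtau, AUClast and CLss/F. The effect is large for that subject (Cmax and AUCtau about 25-27% low for full loss, 12-13% for half) and modest for the summary (about 2.3-2.5% of a 12-profile geometric mean per full-loss profile). The missing condition on the 24 h sample matters mainly for AUClast, at about 7-8% of the geometric mean per truncated profile among 12; for AUCtau it leaves an unspecified extrapolation of uncertain direction.

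The percentages rest on the one-compartment model, the absorption rate and the share of dose lost, all assumed; only the half-life and Tmax range are the protocol's. The mismatch between the documents does not depend on the model. It deserves correction because the profiles are few and serve the bridging comparison, and because the correction is cheap.

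**What to change.** In SAP 2.2 and 2.9, restrict the summaries of Cmax, the AUCs and CLss/F to profiles that meet protocol 8.5.1.1: no vomiting within 4 h of dosing on the sampling day or the day before, and at least six of seven usable samples. Require the 24 h sample for AUCtau, CLss/F and AUClast, and for counting a profile towards the 12. Other profiles stay in the listings, with the reason for exclusion. Substituting the pre-dose value for a missing 24 h value is not advised, since it conflicts with the SAP's rule against imputing PK data.

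SAP 2.9 says that the PK summaries are not reproduced for the final CSR. So first check the existing intensive profiles against this rule. If all pass, a sentence saying so closes the point; if any fails, rerun the summaries without it and state how many profiles remain.

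The cost is a few sentences and one check of the profiles. The downside is possibly one or two fewer profiles in the summaries, with slightly less precision.

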2.2.1 Subgroup of interest

The following subgroups will be considered for outputs. Details of the use of these subgroups will be found in the sections for the relevant endpoints.

The subgroup analysis will not be reproduced for final CSR.

Efficacy

The primary efficacy endpoint will be summarized by the following subgroups:

- Age group (< 65 years) vs. (≥ 65 years)
- Gender : Male vs. Female
- Relapsed patients, refractory patients and patients who achieved PR after the last course of IST with platelet count $<30 \times 10^9 / L$
- Baseline platelet counts: $<20 \times 10^9 / L$, $\geq 20 \times 10^9 / L$
- Prior ATG/ALG Therapies: Yes, No
- Baseline Platelet Transfusion: Independence, Dependence
- Baseline RBC Transfusion: Independence, Dependence
- Concomitant use of CsA and anabolic steroids at baseline: Yes, No

No formal statistical test of hypotheses will be performed for the subgroups, only point estimate of the treatment effect and 90% confidence intervals will be provided if applicable. The objective of the efficacy subgroup analysis is to demonstrate homogeneity of treatment effect in the above subgroups.

Safety

Safety subgroup analyses will use the same method as for the analysis in the overall analysis set. Key safety analyses (all AEs, AEs with suspected relationship to study treatment, SAEs and AESIs) will be repeated on safety set in the following subgroups:

- Age group (< 65 years) vs. (≥ 65 years)
- Gender : Male vs. Female
- Concomitant use of CsA and anabolic steroids at baseline: Yes, No

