2.5.5 Supportive analyses

Subjects can respond according to one or more of three criteria: platelets (platelet counts and/or platelet transfusions), red cells (hemoglobin level and/or RBC transfusions), neutrophils (ANC counts). This results in 7 possible response combinations:

- Platelets
- Red Cells
- Neutrophils
- Platelets/Red Cells
- Platelets/Neutrophils
- Red Cells/Neutrophils
- Platelets/Red Cells/Neutrophils

The number and percentage will be made of the number of subjects who respond according to each combination of criteria at the Week 26 visit.

The number and percentage of assessment item for the detailed hematological response criteria will be presented as follows. In this summary, subjects could be counted as a response according to more than one criteria.

- Platelet Counts in platelet transfusion independent subjects
- Platelet Transfusion in platelet transfusion dependent subjects
- Hemoglobin Level in RBC transfusion independent subjects with baseline hemoglobin level < 90 g/L
- RBC Transfusion in RBC transfusion dependent subjects
- ANC counts

The primary efficacy endpoint will be summarized by the above subgroups listed in [section 2.2.1](#) for efficacy. The proportion of the hematological response in each subgroup will be summarized using point estimates and 90% exact (Clopper-Pearson) confidence intervals if applicable.

In addition, hematological responses will be listed.

The analysis for primary efficacy endpoint will not be reproduced at updated analysis and final analysis.

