2.14 Interim analysis

There will be no formal interim analysis planned in this study.

3 Sample size calculation

As this is a bridging study to support China registration, an estimation strategy rather than formal hypothesis testing will be pursued. Approximately 20 subjects will be enrolled into the study based on the feasibility rather than statistical considerations. This number of subjects is considered appropriate to assess the efficacy and safety of eltrombopag in Chinese patients.

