3.1 Primary analysis

The hematologic response rate at Week 24 in the pivotal study of NIH-09-H-0154 was 40%. Assuming a same response rate (40%) in Chinese subjects, the 90% confidence interval of the hematological response rate with a total of 20 subjects will be (21.7%, 60.6%).

Below table shows the 90% CIs for various observed response rate. The maximum half-width of the 90% CIs is 19.8%.

Table 3-1 90% CIs for various observed response rate

Sample size	# of responders	Hematologic response rate (%)	90% CI (%)
20	4	20	(7.1, 40.1)
20	6	30	(14.0, 50.8)
20	8	40	(21.7, 60.6)

Sample size	# of responders	Hematologic response rate (%)	90% CI (%)
20	10	50	(30.2, 69.8)

The 12 evaluable subjects for intensive PK sampling was chosen based on feasibility and practical considerationzs to assist in characterizing the PK of eltrombopag in Chinese subjects.

4 Change to protocol specified analyses

No change from protocol specified analysis was made.

5 Appendix

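### SAP 2.2.1 aims to demonstrate homogeneity across subgroups, which about 20 subjects over eight factors cannot show

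*SAP*

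**What the plan says.** SAP 2.2.1 introduces the efficacy subgroups with "The primary efficacy endpoint will be summarized by the following subgroups" and lists eight factors: age, gender, disease category (relapsed, refractory, or partial response with low platelets), baseline platelet count, prior ATG/ALG, baseline platelet transfusion status, baseline RBC transfusion status, and concomitant CsA and anabolic steroids. Seven have two levels and one has three, so there are 7 × 2 + 3 = 17 levels.

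On method, the section says "No formal statistical test of hypotheses will be performed for the subgroups" and limits the output to point estimates and 90% intervals. It then gives the purpose: "The objective of the efficacy subgroup analysis is to demonstrate homogeneity of treatment effect in the above subgroups".

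SAP 2.5.5, under supportive analyses, repeats the method: "The proportion of the hematological response in each subgroup will be summarized using point estimates and 90% exact (Clopper-Pearson) confidence intervals if applicable".

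On size, SAP section 3 says "Approximately 20 subjects will be enrolled into the study based on the feasibility rather than statistical considerations" and that "an estimation strategy rather than formal hypothesis testing will be pursued". Neither document gives a homogeneity margin, a between-level contrast, a minimum level size or a rule for declaring homogeneity.

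**The concern.** To demonstrate homogeneity is to show that differences between levels are small. That needs a definition of small and enough data to exclude anything larger. The plan has neither. What remains is a reader setting wide intervals side by side, seeing no clear separation, and taking that as the demonstration. Absence of evidence would then be reported as a pre-specified finding.

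This is a bridging study meant to support registration. A stated aim of demonstrating homogeneity invites text saying that the effect is consistent by age, disease category, prior therapy or transfusion status, and the data cannot carry that.

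Two features of the design add to the difficulty. The study is single-arm, so each level yields a response rate and not a treatment effect. And in SAP Table 2-2 the platelet and hemoglobin criteria depend on baseline transfusion status, so similar rates in transfusion-dependent and independent subjects would not be similar results on one common measure.

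**Working it through.** **Inputs.** From the documents: N about 20; two-sided 90% Clopper-Pearson intervals; an assumed response rate of 40% (SAP 3.1: "Assuming a same response rate (40%) in Chinese subjects"). Assumptions made here: two-level splits of 10/10, 14/6 and 17/3, because the documents give no level sizes; true rates of 60% and 20% as an example of large heterogeneity.

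**Step 1: reproduce the plan's figure.** For x responders out of n, the lower limit is the 5% quantile of Beta(x, n−x+1) and the upper limit is the 95% quantile of Beta(x+1, n−x). For 8/20 this gives (21.7%, 60.6%), and for 10/20 (30.2%, 69.8%), both as in SAP Table 3-1. The largest half-width over all x at n = 20 is 19.8 points, matching "The maximum half-width of the 90% CIs is 19.8".

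**Step 2: the same interval at subgroup size.** The maximum half-width is 28 points at n = 10 and 42 points at n = 3. Near the assumed rate, 4/10 gives (15.0%, 69.6%) and 1/3 gives (1.7%, 86.5%). Even an observed 8/10 against 2/10 gives (49.3%, 96.3%) and (3.7%, 50.7%), which still overlap.

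**Step 3: can large heterogeneity be seen?** For each split, sum Bin(x; n₁, p₁) × Bin(y; n₂, p₂) over all outcomes (x, y) in which the two intervals do not overlap. Do the same for outcomes with a two-sided Fisher p ≤ 0.10. True rates are 60% and 20%.

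| Split | Level with the 60% rate | Intervals do not overlap | Fisher power at 10% |
|---|---|---|---|
| 10/10 | either | 12.9% | 42% |
| 14/6 | larger | 8.9% | 34% |
| 14/6 | smaller | 13.8% | 41% |
| 17/3 | larger | 0.6% | 23% |
| 17/3 | smaller | 6.7% | 34% |

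The Fisher column only illustrates how little information there is; the SAP plans no such test. With a true 40-point difference, the intervals overlap at least 100 − 13.8 = 86.2% of the time.

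**Step 4: does true homogeneity look homogeneous?** With 40% in both levels, sum the probability that |x/n₁ − y/n₂| ≥ 0.20. The result is 49% (10/10), 41% (14/6) and 50% (17/3).

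**Step 5: scale of what would be needed.** For one two-level factor, take 40% in both levels, a 90% interval for the difference that must lie inside ±m, and 80% power. Then n per level = 2 × 0.40 × 0.60 × (1.645 + 1.282)² / m². For an assumed m of 20 points this is 0.48 × 8.57 / 0.04, or 103 per level (206 in total). For m of 30 points it is 0.48 × 8.57 / 0.09, or 46 per level (92 in total). The trial has about 20 in all.

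**The case against.** The strongest defence is that the sentence does little work. The one before it removes testing, the analysis is classed as supportive, and the whole study follows an estimation strategy. Homogeneity is not among the objectives in protocol Table 2-1 or the SAP objectives table, and protocol 12.4.4 contains no subgroup analysis. Wide intervals would be printed beside each rate, so the imprecision would be visible. The subgroup analysis is also not repeated for the final report. All of this is correct and limits the impact. It does not rescue the sentence: without a test or margin, the plan has no means of meeting the objective it sets.

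Four stronger readings are tempting, and the documents do not support them.

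- A reader might infer that response cannot be homogeneous in so small a trial. It may well be; the trial cannot show it.
- A reader might infer that overlapping intervals are assured whatever the truth. They are not: in a 10/10 split, non-overlap occurs 48% of the time at 70% against 10%, and 87% at 90% against 10%.
- A reader might infer that the SAP will judge homogeneity by interval overlap. It names no rule. Overlap is used here as the natural informal reading of the planned output, so the percentages above are not error rates of the plan.
- A reader might infer that a registration conclusion rests on this sentence. No passage says so.

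**Conclusion.** The point holds: SAP 2.2.1 states an objective that its own method and sample size cannot meet. Under the assumed splits, a true 40-point difference separates the two intervals between 0.6% and 13.8% of the time, and equal true rates produce an observed gap of at least 20 points 41% to 50% of the time. The output can therefore mislead in either direction.

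These percentages depend on the assumed level sizes, the example rates and which level has the higher rate. More extreme differences would be seen more often. The conclusion that homogeneity cannot be demonstrated rests on less: about 20 subjects, per-level intervals only, and no margin.

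The effect is confined to what may be concluded from the subgroup table. The primary response rate, its interval and the sample-size rationale do not change. It should be corrected because it bears on how subgroup results are described in a registration study.

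**What to change.** Replace the objective sentence in SAP 2.2.1 with:

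> The objective of the efficacy subgroup analysis is to describe response rates across subgroups, showing n/N and exact 90% CIs; the study is not able to show or exclude heterogeneity, and no conclusion of homogeneity or consistency will be drawn from these results.

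It would also help to replace the open-ended qualifier on when an interval is shown with a stated minimum level size. Because the SAP does not reproduce the subgroup analysis for the final report, the change matters mainly for how the subgroup results from the primary analysis are described, and that wording should follow the revised sentence.

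The cost is one SAP sentence, with no new data, analysis or subjects. The sponsor gives up a homogeneity statement that the data could not have supported.
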